11 PROCEDURES AND INSTRUCTIONS (ADMINISTRATIVE PROCEDURES)

11.1 Changes to the Protocol

Any change to the protocol requires a written protocol amendment or administrative change that must be approved by the sponsor before implementation. Amendments specifically affecting the safety of subjects, the scope of the investigation, or the scientific quality of the study require submission to health or regulatory authorities as well as additional approval by the applicable IRBs/IECs. These requirements should in no way prevent any immediate action from being taken by the investigator, or by the sponsor, in the interest of preserving the safety of all subjects included in the study. If the investigator determines that an immediate change to or deviation from the protocol is necessary for safety reasons to eliminate an immediate hazard to the subjects, the sponsor's medical monitor and the IRB/IEC for the site must be notified immediately. The sponsor must notify the health or regulatory authority as required per local regulations.

Protocol amendments that affect only administrative aspects of the study may not require submission to health or regulatory authority or the IRB/IEC, but the health or regulatory authority and IRB/IEC (or if regionally required the head of the medical institution) should be kept informed of such changes as required by local regulations. In these cases, the sponsor may be required to send a letter to the IRB/IEC and the Competent Authorities (or, if regionally required, the head of the medical institution) detailing such changes.

11.2 Adherence to the Protocol

The investigator will conduct the study in strict accordance with the protocol (refer to ICH E6, Section 4.5).

11.3 Monitoring Procedures

The sponsor's or CRO's CRA will maintain contact with the investigator and designated staff by telephone, letter, or email between study visits. Monitoring visits to each site, and potential remote source document verification, will be conducted by the assigned CRA as described in the monitoring plan. The investigator (or if regionally required, the head of the medical institution) will allow the CRA to inspect the clinical, laboratory, and pharmacy facilities to assure compliance with GCP and local regulatory requirements. The eCRFs and subject's corresponding original medical records (source documents) are to be fully available for review by the sponsor's representatives at regular intervals. These reviews verify adherence to study protocol and data accuracy in accordance with local regulations. All records at the site are subject to inspection by the local auditing agency and to IRB/IEC review.

In accordance with ICH E6, Section 1.52, source documents include, but are not limited to, the following:

- Clinic, office, or hospital charts
- Copies or transcribed health care provider notes that have been certified for accuracy after production
- Recorded data from automated instruments such as IxRS, x-rays, and other imaging reports (eg, sonograms, computed tomography scans, MRIs, radioactive images, ECGs, rhythm strips, electroencephalography, polysomnographs, pulmonary function tests) regardless of how these images are stored, including microfiche and photographic negatives
- Pain, quality of life, or medical history questionnaires completed by subjects
- Records of telephone contacts
- Diaries or evaluation checklists
- Drug distribution and accountability logs maintained in pharmacies or by research personnel
- Laboratory results and other laboratory test outputs (eg, urine pregnancy test result documentation and urine dip-sticks)
- Correspondence regarding a study subject's treatment between physicians or memoranda sent to the IRBs/IECs
- CRF components (eg, questionnaires) that are completed directly by subjects and serve as their own source

11.4 Recording of Data

An eCRF is required and must be completed for each subject by qualified and authorized personnel. All data on the eCRF must reflect the corresponding source document, except when a section of the eCRF itself is used as the source document. Any correction to entries made on the eCRF must be documented in a valid audit trail where the correction is dated, the individual making the correction is identified, the reason for the change is stated, and the original data are not obscured. Only data required by the protocol for the purposes of the study should be collected.

The investigator must sign each eCRF. The investigator will report the eCRFs to the sponsor and retain a copy of the eCRFs.

11.5 Identification of Source Data

All data to be recorded on the eCRF must reflect the corresponding source documents.

11.6 Retention of Records

The circumstances of completion or termination of the study notwithstanding, the investigator (or if regionally required, the head of the medical institution or the designated representative) is responsible for retaining all study documents, including but not limited to the protocol, copies of eCRFs, the Investigator's Brochure, and regulatory agency registration documents (eg, Form FDA 1572, ICFs, and IRB/IEC correspondence). The site should plan to retain study documents, as directed by the sponsor, for at least 2 years after the last approval of a marketing application in an ICH region and until there are no pending or contemplated marketing applications in an ICH region or at least 3 years have elapsed since the formal discontinuation of clinical development of the investigational product.

It is requested that at the completion of the required retention period, or should the investigator retire or relocate, the investigator contact the sponsor, allowing the sponsor the option of permanently retaining the study records.

11.7 Auditing Procedures and Inspection

In addition to routine monitoring procedures, the sponsor's Clinical Quality Assurance department conducts audits of clinical research activities in accordance with the sponsor's standard operating procedures to evaluate compliance with the principles of ICH GCP and all applicable local regulations. If a government regulatory authority requests an inspection during the study or after its completion, the investigator must inform the sponsor immediately.

11.8 Handling of Study Drug

All study drug will be supplied to the principal investigator (or a designated pharmacist) by the sponsor. Drug supplies must be kept in an appropriate secure area (eg, locked cabinet) and stored according to the conditions specified on the drug labels. The investigator (or a designated pharmacist) must maintain an accurate record of the shipment and dispensing of the study drug in a drug accountability ledger, a copy of which must be given to the sponsor at the end of the study. An accurate record of the date and amount of study drug dispensed to each subject must be available for inspection at any time. The CRA will visit the site and review these documents along with all other study conduct documents at appropriate intervals once study drug has been received by the site.

All drug supplies are to be used only for this study and not for any other purpose. The investigator (or site personnel) must not destroy any drug labels or any partly used or unused drug supply before approval to do so by the sponsor. At the conclusion of the study and as appropriate during the study, the investigator (or a designated pharmacist) will return all used and unused drug containers, drug labels, and a copy of the completed drug disposition form to the sponsor's CRA (or designated contractor).

11.9 Publication of Results

All manuscripts, abstracts, or other modes of presentation arising from the results of the study must be reviewed and approved in writing by the sponsor in advance of submission pursuant to the terms and conditions set forth in the executed CTA between the sponsor/CRO and the institution/investigator. The review is aimed at protecting the sponsor's proprietary information existing either at the date of the commencement of the study or generated during the study. The detailed obligations regarding the publication of any data, material results, or other information generated or created in relation to the study shall be set out in the agreement between each investigator and the sponsor or CRO, as appropriate.

11.10 Disclosure and Confidentiality

The contents of this protocol and any amendments and results obtained during the study should be kept confidential by the investigator, the investigator's staff, and the IRB/IEC and will not be disclosed in whole or in part to others, or used for any purpose other than reviewing or performing the study, without the written consent of the sponsor. No data collected as part of this study will be used in any written work, including publications, without the written consent of the sponsor. These obligations of confidentiality and non-use shall in no way diminish such obligations as set forth in either the Confidentiality Agreement or CTA executed between the sponsor/CRO and the institution/investigator. All persons assisting in the performance of this study must be bound by the obligations of confidentiality and non-use set forth in either the Confidentiality Agreement or CTA executed between the institution/investigator and the sponsor/CRO.

11.11 Discontinuation of Study

The sponsor reserves the right to discontinue the study for medical reasons or any other reason at any time. If a study is prematurely terminated or suspended, the sponsor will promptly inform the investigators/institutions and regulatory authorities of the termination or suspension and the reason(s) for the termination or suspension. The IRB/IEC will also be informed promptly and provided the reason(s) for the termination or suspension by the sponsor or by the investigator/institution, as specified by the applicable regulatory requirement(s).

The investigator reserves the right to discontinue the study should his/her judgment so dictate. If the investigator terminates or suspends a study without prior agreement of the sponsor, the investigator should inform the institution where applicable, and the investigator/institution should promptly inform the sponsor and the IRB/IEC and provide the sponsor and the IRB/IEC with a detailed written explanation of the termination or suspension. Study records must be retained as noted [above](#).

11.12 Subject Insurance and Indemnity

The sponsor will provide insurance for any subjects participating in the study in accordance with all applicable laws and regulations.

12 APPENDICES

Appendix 1 Sponsor's Grading for Laboratory Values

(revised per Amendment 01)

| | Grade 1 | Grade 2 | Grade 3 | Grade 4 |
|--|---|---|---|---|
| BLOOD/BONE MARROW | | | | |
| Hemoglobin (conversion from g/dL×0.6206) | Female (ULN=15.9 g/dL) <11.1 – 10.0 g/dL <111 – 100 g/L <6.9 – 6.2 mmol/L Male (ULN=17.7 g/dL) <12.6 – 10.0 g/dL <126 – 100 g/L <7.8 – 6.2 mmol/L | <10.0 – 8.0 g/dL <100 – 80 g/L <6.2 – 4.9 mmol/L | <8.0 g/dL <80 g/L <4.9 mmol/L; transfusion indicated | life-threatening consequences; urgent intervention indicated |
| Leukocytes (total white blood cell) | <3.40 – 3.0×10 ⁹ /L <3.40 10 ³ /uL – 3000/mm ³ (ULN=10.80 10 ³ /μL) | <3.0 – 2.0×10 ⁹ /L <3000 – 2000/mm ³ | <2.0 – 1.0×10 ⁹ /L <2000 – 1000/mm ³ | <1.0×10 ⁹ /L <1000/mm ³ |
| Lymphocytes | not applicable | <700 – 500/mm ³ <0.7 – 0.5×10 ⁹ /L | <500 – 200/mm ³ <0.5 – 0.2×10 ⁹ /L | <200/mm ³ <0.2×10 ⁹ /L |
| Neutrophils | not applicable | <1.4 – 1.0×10 ⁹ /L <1400 – 1000/mm ³ | <1.0 – 0.5×10 ⁹ /L <1000 – 500/mm ³ | <0.5×10 ⁹ /L <500/mm ³ |
| Platelets | <155 – 75.0×10 ⁹ /L <155 10 ³ /uL – 75,000/mm ³ (ULN=379 10 ³ /μL) | <75.0 – 50.0×10 ⁹ /L <75,000 – 50,000/mm ³ | <50.0 – 25.0×10 ⁹ /L <50,000 – 25,000/mm ³ | <25.0×10 ⁹ /L <25,000/mm ³ |
| METABOLIC/LABORATORY | | | | |
| Albumin, serum- low (hypoalbuminemia) | 2 - 59 years (ULN=5.5 g/dL) <3.5 – 3 g/dL <35 – 30 g/L 59 -69 years (LLN-ULN) <3.6 g/dL – 3 g/dL 69 -79 years (LLN-ULN) <3.5g/dL – 3g/dL 79 -89 years (LLN-ULN) <3.5g/dL – 3g/dL | <3 – 2 g/dL <30 – 20 g/L | <2 g/dL <20 g/L | life-threatening consequences; urgent intervention indicated |
| Alkaline phosphatase | Female: 18 -19 years >101 – 3.0×101 19 -61 years ULN=107 61 -71 years ULN=112 71 -150 years ULN=108 Male 18 -19 years >127 – 3.0×127 19 -61 years ULN=102 61 -71 years ULN=103 71 -150 years ULN=105 | >3.0 – 5.0×ULN See previous column for ULN values | >5.0 – 20.0×ULN See previous column for ULN values | >20.0×ULN See previous column for ULN values |
| Alanine aminotransferase | Female: >32 – 3.0×32 Male: >44 – 3.0 x 44 | Female: >3.0 – 5.0×32 Male >3.0 – 5.0×44 | Female: >5.0 – 20.0×32 Male: >5.0 – 20.0×44 | Female: >20.0×32 Male: >20.0×44 |

| | Grade 1 | Grade 2 | Grade 3 | Grade 4 |
|--|--|--|---|--|
| Aspartate aminotransferase | >40 – 3.0×40 | >3.0 – 5.0×40 | >5.0 – 20.0×40 | >20.0×40 |
| Bilirubin (hyperbilirubinemia) | >1.2 – 1.5×1.2 | >1.5 – 3.0×1.2 | >3.0 – 10.0×1.2 | >10.0×1.2 |
| Calcium, serum-low (hypocalcemia) (conversion to mmol×0.25) | <8.5 – 8.0 mg/dL <2.13 – 2.0 mmol/L | <8.0 – 7.0 mg/dL <2.0 – 1.75 mmol/L | <7.0 – 6.0 mg/dL <1.75 – 1.5 mmol/L | <6.0 mg/dL <1.5 mmol/L |
| Calcium, serum-high (hypercalcemia) | >10.6 – 11.5 mg/dL >2.65 – 2.9 mmol/L | >11.5 – 12.5 mg/dL >2.9 – 3.1 mmol/L | >12.5 – 13.5 mg/dL >3.1 – 3.4 mmol/L | >13.5 mg/dL >3.4 mmol/L |
| Cholesterol, serum-high (hypercholesterolemia) (conversion to mmol/L ×0.02586) | 0 -19 years >169 – 300 mg/dL >4.37 – 7.75 mmol/L 19 -150 years >199 – 300 mg/dL >5.15 – 7.75 mmol/L | >300 – 400 mg/dL >7.75 – 10.34 mmol/L | >400 – 500 mg/dL >10.34 – 12.92 mmol/L | >500 mg/dL >12.92 mmol/L |
| Creatinine | Female >1.00 mg/dL – 1.5×1.00 Male >1.27 mg/dL – 1.5×1.27 | Female >1.5 – 3.0×1.00 Male >1.5 mg/dL – 3.0×1.27 | Female >3.0 – 6.0×1.00 Male >3.0 mg/dL – 6.0 ×1.27 | Female >6.0×1.00 Male >6.0×1.27 |
| Gamma glutamyl transpeptidase | Female >60 IU/L – 3.0×60 Male >65 IU/L – 3.0×65 | Female >3.0 – 5.0×60 Male >3.0 – 5.0×65 | Female >5.0 – 20.0×60 Male >5.0 – 20.0×65 | Female >20.0×60 Male >20.0×65 |
| Glucose, serum-high (hyperglycemia) (conversion to mmol/L ×0.0555) | Fasting glucose value >99 – 160 mg/dL >5.5 – 8.9 mmol/L | Fasting glucose value >160 – 250 mg/dL >8.9 – 13.9 mmol/L | >250 – 500 mg/dL; >13.9 – 27.8 mmol/L; hospitalization indicated | >500 mg/dL; >27.8 mmol/L; life-threatening consequences |
| Glucose, serum-low (hypoglycemia) | <65 – 55 mg/dL <3.6 – 3.0 mmol/L | <55 – 40 mg/dL <3.0 – 2.2 mmol/L | <40 – 30 mg/dL <2.2 – 1.7 mmol/L | <30 mg/dL <1.7 mmol/L life-threatening consequences; seizures |
| Phosphate, serum-low (hypophosphatemia) (conversion to mmol/L ×0.323) | not applicable | <2.5 – 2.0 mg/dL <0.8 – 0.6 mmol/L | <2.0 – 1.0 mg/dL <0.6 – 0.3 mmol/L | <1.0 mg/dL <0.3 mmol/L life-threatening consequences |
| Potassium, serum-high (hyperkalemia) | not applicable | >5.5 – 6.0 mmol/L | >6.0 – 7.0 mmol/L hospitalization indicated | >7.0 mmol/L life-threatening consequences |
| Potassium, serum-low (hypokalemia) | <3.5 mEq/L – 3.0 mmol/L | <LLN – 3.0 mmol/L; symptomatic; intervention indicated | <3.0 – 2.5 mmol/L hospitalization indicated | <2.5 mmol/L life-threatening consequences |
| Sodium, serum-high (hypernatremia) | >144 mEq/L – 150 mmol/L | >150 – 155 mmol/L | >155 – 160 mmol/L hospitalization indicated | >160 mmol/L life-threatening consequences |
| Sodium, serum-low (hyponatremia) | <134 mEq/L – 130 mmol/L | Not applicable | <130 – 120 mmol/L | <120 mmol/L life-threatening consequences |
| Triglyceride, serum-high (hypertriglyceridemia) | 150 – 300 mg/dL 1.71 – 3.42 mmol/L | >300 – 500 mg/dL >3.42 – 5.7 mmol/L | >500 – 1000 mg/dL >5.7 – 11.4 mmol/L | >1000 mg/dL >11.4 mmol/L life-threatening consequences |

| | Grade 1 | Grade 2 | Grade 3 | Grade 4 |
|---------------------------------------|--|----------------|--|--|
| Uric acid, serum-high (hyperuricemia) | Female >7.1 – 10 mg/dL Male >8.6 – 10 mg/dL Both ≤0.59 mmol/L without physiologic consequences | Not applicable | Female >7.1 – 10 mg/dL Male >8.6 – 10 mg/dL Both ≤0.59 mmol/L without physiologic consequences | >10 mg/dL >0.59 mmol/L life-threatening consequences |

LLN = lower limit of normal, ULN = upper limit of normal.

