9.5.1.5.3 LABORATORY MEASUREMENTS

Clinical laboratory tests to be performed, including hematology, chemistry, urinalysis, and CSF are summarized in Table 4. Subjects should be in a seated or supine position during blood collection. Table 6 and Table 7 show the visits and time points at which blood for clinical laboratory tests and urine for urinalysis will be collected in the study.

See Section 9.3.3 for safety criteria for discontinuation from study drug related to absolute counts of CD4, CD8, and B lymphocytes, and for lymphocyte subset counts.

Table 4 Clinical Laboratory Tests

| Category | Parameters |
|-----------------------------|---|
| Hematology | Hematocrit, hemoglobin, platelets, red blood cell count, and white blood cell count with differential (bands, basophils, eosinophils, lymphocytes, monocytes, neutrophils), and (Screening and Baseline only), PT, PTT, and INR |
| Chemistry | |
| Electrolytes | Bicarbonate, calcium, chloride, phosphate, potassium, sodium |
| Liver function tests | Alanine aminotransferase, alkaline phosphatase, aspartate aminotransferase, gamma glutamyl transpeptidase, direct bilirubin, total bilirubin |
| Renal function tests | Blood urea/blood urea nitrogen, creatinine |
| Other | Albumin, cholesterol, globulin, glucose, lactate dehydrogenase, total protein, triglycerides, uric acid |
| Urinalysis | Bacteria, casts, crystals, epithelial cells, glucose, ketones, occult blood, pH, protein, red blood cells, specific gravity, white blood cells |
| Other | Lymphocyte subset analyses (see Table 5). Regulatory T cells will be measured using CD4, CD25, and CD127 cell surface markers and FoxP3 intracellular marker. PBMCs Ig analyses (IgG, IgA, and IgM). Viral screen (HCVAb [Hepatitis C] and HBsAg [Hepatitis B]). Viral characterization (including HSV1, HSV2 and CMV, etc) Serum pregnancy test (females of child bearing potential only) Tuberculosis Interferon Gamma Release Assays Tests for thyroid function (thyroid stimulating hormone, free triiodothyronine and free thyroxine) and vitamin B12 Blood sample for storage for subsequent testing of immune status Cerebrospinal fluid sampling |

CMV = cytomegalovirus, HBsAg = hepatitis B surface antigen, HCVAb = hepatitis C virus antibody, HSV = herpes simplex virus, Ig = immunoglobulin, INR = International Normalized Ratio, PBMC = peripheral blood mononuclear cell, PT = prothrombin time, PTT = partial thromboplastin time.

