9.7.1.8.3 LABORATORY VALUES

Laboratory results will be summarized using International System of Units, as appropriate. For all quantitative parameters listed in [Section 9.5.1.5.3](#), the actual value and the change from baseline to each postbaseline visit and to the end of treatment (defined as the last on-treatment value) will be summarized by visit and treatment group using descriptive statistics. Qualitative parameters listed in [Section 9.5.1.5.3](#) will be summarized using frequencies (number and percentage of subjects), and changes from baseline to each postbaseline visit and to end of treatment will be reported using shift tables. Percentages will be based on the number of subjects with both nonmissing baseline and relevant postbaseline results.

Laboratory test results will be assigned a low/normal/high (LNH) classification according to whether the value was below (L), within (N), or above (H) the laboratory parameter's reference range. Within-treatment comparisons for each laboratory parameter will be based on 3-by-3 tables (shift tables) that compare the baseline LNH classification to the LNH classification at each postbaseline visit and at the end of treatment. Similar shift tables will also compare the baseline LNH classification to the LNH classification for the highest and lowest value during the treatment period.

[Appendix 1](#) (Sponsor's Grading for Laboratory Values) presents the criteria that will be used to identify subjects with treatment-emergent markedly abnormal laboratory values

(TEMAVs). Except for phosphate, a TEMAV is defined as a postbaseline value with an increase from baseline to a Grade of 2 or higher. For phosphate, a TEMAV was defined as a postbaseline value with an increase from baseline to a Grade of 3 or higher. When displaying the incidence of TEMAVs, each subject may be counted once in the laboratory parameter high and in the laboratory parameter low categories, as applicable.

Lymphocyte subsets (ie, CD4 [T helper cells], CD8 [cytotoxic T cells], CD19 [B cells], CD16/CD56 [natural killer cells] and CD14 [macrophages]) and regulatory T cells will be summarized in the same manner as other laboratory parameters. Mean lymphocyte subsets and the mean change from baseline in lymphocyte subsets will also be displayed graphically over time by dose.

Serum IgG, IgM, and IgA will be measured and summarized in the same manner as other laboratory parameters.

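### Appendix 1 gives uric acid Grade 1 and Grade 3 the same criterion, so a subject newly entering that band is both a TEMAV and not a TEMAV

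*Protocol*

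**What the plan says.** The high uric acid row of Appendix 1 (Sponsor's Grading for Laboratory Values) reads as follows.

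- Grade 1: "Female >7.1 – 10 mg/dL Male >8.6 – 10 mg/dL Both ≤0.59 mmol/L without physiologic consequences"
- Grade 2: marked as not applicable
- Grade 3: the same words as Grade 1, including the closing qualifier "Both ≤0.59 mmol/L without physiologic consequences"
- Grade 4: ">10 mg/dL >0.59 mmol/L life-threatening consequences"

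The row is the same in both copies of the appendix in the document: the Version 3.0 copy, and a later copy whose Appendix 2 carries Amendment 02 changes.

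Section 9.7.1.8.3 (Laboratory Values) says that Appendix 1 supplies the TEMAV criteria. It then gives the rule: "Except for phosphate, a TEMAV is defined as a postbaseline value with an increase from baseline to a Grade of 2 or higher". The only exception is "For phosphate, a TEMAV was defined as a postbaseline value with an increase from baseline to a Grade of 3 or higher". Uric acid has none. It is a scheduled test, listed in Table 4 of Section 9.5.1.5.3 among the other chemistry parameters: "Albumin, cholesterol, globulin, glucose, lactate dehydrogenase, total protein, triglycerides, uric acid".

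**The concern.** A grading table has to send each value to one grade. Here one value meets two grades that are two levels apart, and the TEMAV threshold of Grade 2 lies between them. With Grade 2 unused for uric acid, the Grade 3 cell alone decides whether a raised value at or below 10 mg/dL counts as markedly abnormal, and that cell repeats Grade 1.

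At stake is whether the reported uric acid TEMAV incidence can be reproduced. Two programmers following the protocol faithfully could produce different counts in every arm, and neither would be in breach of it. The protocol has not left this matter to the statistical analysis plan: it fixes the criteria in its own appendix, and a plan that copies the table inherits the contradiction.

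**Working it through.** The plan states no figure to reproduce. The check codes the uric acid row and the TEMAV rule as printed and applies both possible readings.

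**Inputs**
- Upper limit of normal (ULN): 7.1 mg/dL female, 8.6 mg/dL male (Appendix 1).
- ULN < value ≤ 10 mg/dL: meets Grade 1 and Grade 3 (Appendix 1).
- Value > 10 mg/dL: Grade 4 (Appendix 1).
- TEMAV: post-baseline grade ≥ 2 and higher than the baseline grade (Section 9.7.1.8.3).

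**Newly entering the band from a normal baseline**, in steps of 0.1 mg/dL:
- Female grid, 7.2 to 10.0: (10.0 − 7.2)/0.1 + 1 = 29 values.
- Male grid, 8.7 to 10.0: (10.0 − 8.7)/0.1 + 1 = 14 values.

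| Reading | Grade in band | Female flagged | Male flagged |
|---|---|---|---|
| Lower matching grade | 1 | 0 of 29 | 0 of 14 |
| Higher matching grade | 3 | 29 of 29 | 14 of 14 |

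**Other paths**
- Baseline in the band, later value in the band (for example female 8 to 9, male 9 to 9.9): the grade does not rise, so neither reading flags it.
- Baseline normal or in the band, later value above 10 (for example female 6 to 10.1, or 8 to 10.1): Grade 4, flagged under both readings.

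The ambiguity therefore sits only with subjects who enter the band after a normal baseline.

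**Is the overlap deliberate?** Two other rows of the table suggest not.
- Low sodium also has no Grade 2, but its Grade 1 (below 134 down to 130) and Grade 3 (below 130 down to 120 mmol/L) are different ranges.
- Low potassium has Grades 1 and 2 over the same numerical band, but a requirement for symptoms and intervention separates them.

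In the uric acid row both the range and the qualifier are repeated. Because both cells require the absence of physiologic consequences, a value in the band that does have consequences matches no grade as printed.

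**The case against.** The strongest reply is that little depends on this row, and that is largely right. Section 9.7.1.8 summarises safety descriptively. The study-drug discontinuation criteria in Section 9.3.3 do not mention uric acid, and the safety objective singles out immunological and hematological parameters. Section 9.7.1.8.3 also requires values and changes from baseline by visit, and low/normal/high shift tables that include the highest and lowest value on treatment. A rise above the reference range stays visible whichever cell is used. A reader might infer that a key threshold of the safety objective is broken; the documents do not support that.

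Three other limits stand.

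- A reader might infer that all or none of the subjects in the band are flagged. The rule requires a rise in grade from baseline, so subjects who are in the band at baseline and stay there are flagged under neither reading.
- The TEMAV text shown is in the Version 3.0 body, which pairs with the Version 3.0 appendix. The body that goes with the later appendix copy is not in the part at hand, so the consequence is demonstrated for Version 3.0 and only inferred for the later version.
- A reader might infer that counting only values above 10 mg/dL is a safe interim rule. That treats the whole band as Grade 1 and discards the printed Grade 3 cell, and nothing in the documents supports the choice.

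A fault in reading the PDF is unlikely, because two separately laid-out copies agree. The Version 3.0 revision history records corrections to several analytes in this appendix to match the central laboratory's grading. Uric acid is not among them, so that record does not settle which wording was meant.

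**Conclusion.** The inconsistency is real and minor. As printed in Version 3.0, a subject whose uric acid rises from normal to above 7.1 (female) or 8.6 (male) but not above 10 mg/dL is both Grade 1, which is not a TEMAV, and Grade 3, which is. The TEMAV count from this band can be anything from none to all of the newly entering subjects. How many that would be cannot be derived, since the documents give no distribution of uric acid.

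The conclusion rests on the row being as printed in both copies and on no tie-break being stated elsewhere in the text shown. It reaches one row of a descriptive laboratory table, and no efficacy analysis or treatment rule.

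**What to change.** Before unblinding, check the uric acid Grade 1 and Grade 3 cells of Appendix 1 against the sponsor's grading source and correct them so that they can be told apart. Alternatively, state in Section 9.7.1.8.3 or the statistical analysis plan which grade applies for TEMAV counting when a value meets both. While the row is open, say also how a value in the band with physiologic consequences is graded. Do not adopt a provisional cut-off in the meantime, since any cut-off would pick one reading without support. The cost is one table cell or one sentence, with no effect on data collection or sample size.
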